	
the enrolment of next patient will not be stopped. The two-stage design is planned to stop further recruitment of patient if the defined efficacy boundary (see Table 7.7.2: 1) is not met at the first stage.
 
The interim analyses for each cohort will be conducted after 15th patients in that cohort have completed their two on-treatment imaging assessment (i.e. end of cycle 4).
 
In addition, if considered necessary interim analysis may be performed for evaluation of the efficacy and safety aspects as each cohort is finished.
 
To:
 
In Part 2, 230 patients are planned to be treated. 40 patients each are planned for cohorts A and B, and 30 patients each are planned for cohorts C, D, E, F, and G. An interim futility analysis will be performed for cohorts C, D, E, F, and G in Part 2. The interim analyses for each cohort are planned to be conducted after 15 patients in that cohort have completed their two on-treatment imaging assessments (i.e., end of cycle 4). For each cohort, timing of the interim analysis may be adjusted according to actual recruitment rate to facilitate or avoid delay of the trial conduct. Until any decision from the futility analysis is done, the enrollment of next patient will not be stopped. The two-stage design is planned to stop further recruitment of patients if the defined efficacy boundary (see Table 7.7.2: 1) is not met at the first stage.

Section to be changed	Adaptions regarding new cohort
Section to be changed	7.7.2 Determination of sample size for Part 2
Description of change	
Change from:
 
• Cohort F: patients with locally advanced or metastatic and/or unresectable Hepatocellular Carcinoma (HCC) who were intolerant or progressed during 1st line sorafenib or lenvatinib treatment; subsequent CPI therapy is allowed as the most recent anticancer treatment. 
.....
 
For cohort D (GBM), around 25% ORR with Bevacizumab is assumed. In AVF3708 (R11-2708), which is an open-label study in patients with glioblastoma who had progressed following initial treatment with temozolomide and radiation, the ORR was 28% [95%CI, 19-40] (N=85). Based on above results, the futility boundary for cohort D is set as 25% at planned interim futility analysis timing.

For cohort F (HCC), around 15% ORR with anti-PD-1 antibody monotherapy is assumed. In Checkmate-040 ([R17-3829](#)) which is an open label phase I/II trial of Nivolumab in patients with advanced hepatocellular carcinoma, the ORR was 20% [95%CI, 15-26] (N=50) in dose expansion phase and 15% [95% CI, 6-28] (N=10) in the dose escalation phase. In KEYNOTE-224 ([R19-0168](#)) which is a phase 2 study of Pembrolizumab in patients with advanced hepatocellular carcinoma previously treated with sorafenib, the ORR was 17% [95% CI, 11-26] (N=104). Based on above result, the futility boundary for cohort F is set as 15% at planned interim futility analysis timing. Different homogeneous scenarios and heterogeneous scenarios as well as different sample sizes are considered in the simulations to assess the operating characteristics of the BHM approach. The simulation results as shown in [Table 7.7.2: 2](#) below show that, with the proposed cohort size, the BHM approach has reasonable probability of reaching the pre-specified response rate under a wide range of scenarios.

To:

Cohort F (2nd line HCC): patients with locally advanced or metastatic and/or unresectable Hepatocellular Carcinoma who were intolerant or progressed during 1st line sorafenib or lenvatinib treatment; ~~subsequent CPI therapy is allowed as the most recent anticancer treatment~~.

- Cohort G (1st line HCC): patients with locally advanced or metastatic and/or unresectable HCC with no prior systemic treatment

A total of approximately 230 patients will be enrolled for these 7 cohorts. 40 patients each are planned for cohorts A and B, and 30 patients each are planned for cohorts C to G

....

For cohort D (GBM), around 20% ORR with Bevacizumab is assumed. In a recent phase II study ([R22-0513](#)) comparing standard dose bevacizumab versus low dose bevacizumab plus lomustine, in patients with recurrent glioblastoma following standard radiation and temozolomide, the ORR was 19% [95% CI, 8-36] (N = 36) based on RANO criteria for the standard dose bevacizumab arm. Based on above results, the futility boundary for cohort D is set as 20% at planned interim futility analysis timing.

For cohort F (2nd line HCC), around 15% ORR with anti-PD-1 antibody monotherapy is assumed. In Checkmate-040 ([R17-3829](#)) which is an open label phase I/II trial of Nivolumab in patients with advanced hepatocellular carcinoma, the ORR was 20% [95% CI, 15-26] (N=50) in dose expansion phase and 15% [95% CI, 6-28] (N=10) in the dose escalation phase. In KEYNOTE-224 ([R19-0168](#)) which is

	
a phase 2 study of Pembrolizumab in patients with advanced hepatocellular carcinoma previously treated with sorafenib, the ORR was 17% [95% CI, 11-26] (N=104). Based on above result, the futility boundary for cohort F is set as 15% at planned interim futility analysis timing.
 
For cohort G (1st line HCC), around 20% ORR with target monotherapies is assumed. In REFLECT (R20-3051), which is a Phase 3 study comparing Lenvatinib vs. Sorafenib, the ORR was 19% [95%, CI 17-21] (N = 478) for Lenvatinib and 7% [95%, CI 6-8] (N = 476) for Sorafenib. In IMbrave150 (R22-0533), which is a Phase III trial comparing Atezolizumab plus Bevacizumab vs. Sorafenib, the ORR for Sorafenib arm observed was 12% [95% CI, 7-17] (N = 165). In Checkmate-459 (R22-0532), which is a phase III study comparing Nivolumab vs. Sorafenib, the observed ORR was 7% [95% CI, 4-10] (N = 372)). Based on above result, the futility boundary for cohort G is set as 20% at planned interim futility analysis timing.
 
Proposed sample size will provide accumulative safety and tolerability data for the investigational combination across different tumor types. Different homogeneous scenarios and heterogeneous scenarios as well as different sample sizes are considered in the simulations to assess the operating characteristics of the BHM approach. The simulation results as shown in Table 7.7.2: 2 below show that, with the proposed cohort size and interim futility analysis in SCLC, MLN, GBM and HCC cohorts, the BHM approach has reasonable probability of reaching the pre-specified response rate under a wide range of scenarios. The probability of observing a $\geq 15\%$ increase in the shrinkage estimator of the ORR under negative scenario is well controlled on cohort level (< 1%). Desirable true positive probabilities ($\sim 60\%$) and false negative probabilities (<2%) are also demonstrated under nugget scenarios for each cohort on proposed sample size.
 
Additional update of:
 
Table 7.7.2: 1 Early stopping probabilities at interim for cohorts C-G based on observed ORR under different scenarios
 
Table 7.7.2: 2 Operating characteristics of the Bayesian Hierarchical Modelling approach for final analysis under different scenarios with futility evaluation at the interim

Rationale for change	Adaptions regarding new cohort and patient numbers.
Section to be changed	9.1
Description of change	Added information:

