	
In the dose expansion study, only dose reductions are allowed for BI 836880.
 
Table 4.1.4: 3 Dose reduction recommendations for BI 836880 in Part 2
 

BI 836880 received dose	BI 836880 reduced dose	

720 mg	480 mg	

 
A dose reduction of BI 836880 from 720 mg to 480 mg is allowed, if investigator can attribute the AE unequivocally to the BI 836880 (for eg., hypertension). If the reduced dose is still intolerable, the dose maybe delayed (please see below the sub-section “Delay of treatment”). Where deemed in the best interest of the patient, the investigator may restart at the originally assigned dose of 720 mg of BI 836880 as soon as deemed clinically appropriate.
 
Delay of Treatment:
 
During combination therapy, if treatment is held or discontinued due to an AE(s), both BI 836880 and BI 754091 will be held or discontinued together. If treatment is to be restarted after resolution (\leq Grade 1 or baseline) of the AE, both BI 836880 and BI 754091 must be started together. The combination therapy may be delayed for up to 6 weeks because of AEs, following discussion with the sponsor.
	BI 836880 received dose	BI 836880 reduced dose	720 mg	480 mg
BI 836880 received dose	BI 836880 reduced dose				
720 mg	480 mg				
Rationale for change	Changes refer to the possibility to down dithrate the dose for the patients in case of AEs.				
Section to be changed	4.2.2 Restrictions				
Description of change	
Changed from:
 
Concomitant anti-cancer therapy is not allowed. Radiotherapy for local symptom control of non-target lesions can be allowed after consulting the investigator and sponsor. 
To:
 
Concomitant anti-cancer therapy is not allowed. Radiotherapy for local symptom control of non-target lesions can be allowed after consulting the investigator and sponsor. Palliative radiotherapy will not be allowed during the first cycle for any lesion. Palliative radiotherapy is allowed only for non-target lesions, following discussion with the Medical Monitor, provided that the reason for radiotherapy does not reflect PD and does not interfere with response assessment. Lesions that have been exposed to radiotherapy are no longer evaluable, and may not be included in the assessment of the non-target lesions and the overall assessment. Unless in emergency
				

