	Male patients with partners of childbearing potential must agree to use condoms and ensure their partner is using an additional highly-effective method of birth control, during the trial and until at least 6 months after the end of the trial treatment.
Rationale for change	Adaption to clarify the information regarding restrictions regarding women of childbearing potential.
Section to be changed	5.1 Assessment of Efficacy
Description of change	
Added information:
 
The same method of assessment and the same technique should be used also in follow up of identified and reported lesions. Lesions in previously irradiated areas may not be used as target lesions (except recurrent glioblastoma after a period of 12 weeks). Baseline evaluation must be performed as close as possible to the treatment start and no more than 28 days before start of treatment.
 
Efficacy endpoints will be assessed every 2 cycles (6 weeks) as specified in the FC. An additional evaluation at EoT is only applicable; when patient has no PD documented, will not continue with regular imaging in Follow-up period and did not have imaging within the last 4 weeks before EoT. At Safety Follow-up visit, in case a patient has discontinued due to PD one additional tumor assessment should be done in case no other cancer treatment has been initiated. All measurements must be recorded in metric notation.
 
All tumor imaging performed in this trial will be collected by authorized CRO and stored until shipment to Boehringer Ingelheim. The CRO will not be implicated in tumor response evaluation. This collected data may be considered for central review at a later time point.
 
Additionally added:
 
5.1.1 Tumor response assessments using RECIST 1.1
 
5.1.2 Tumor response assessments using RANO
 
Including the RANO criteria

Rationale for change	To address the evaluation regarding the Glioblastoma cohort
Section to be changed	5.2.1 Physical examination
Description of change	Change from: A complete physical examination (including cardiac, neurological, dermatological, pulmonological etc.), record of height (only at screening visit), weight and ECOG performance score will be performed at screening and before start of treatment and EoT and EoR. At further time points specified in the FC not a complete PE must be done, but at minimum the actual health status of the patient

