Description of change	
Changed from: For the determination of the MTD, only MTD-evaluable patients will be considered. For the analysis of secondary and further endpoints, all patients in the treated set (i.e., patients treated with at least one dose of trial medication) will be included in the analysis. Any other analysis
 
To: For the determination of the MTD, only MTD-evaluable patients will be considered. For the analysis of secondary and further endpoints in Part 1, all patients in the treated set (i.e., patients treated with at least one dose of trial medication) will be included in the analysis. All analyses planned in Part 2 will be based on the treated set.

Rationale for change	Adapted wording regarding Part 2.
Section to be changed	7.3.1.2 Primary endpoint analyses for Part 2
Description of change	
Change from: The primary endpoint for Part 2 of the trial is OR defined by confirmed CR or PR according to RECIST 1.1 as assessed by the Investigator. Overall response will be analyzed in terms of the shrinkage estimator of the OR rate (ORR) based on BHM.
 
To: The primary endpoint for Part 2 of the trial is OR defined by confirmed CR or PR according to RECIST 1.1 for all cohorts except GBM as assessed by the Investigator. OR in GBM cohort will be evaluated using RANO criteria. Overall response will be analyzed in terms of the shrinkage estimator of the OR rate (ORR) based on BHM.

Rationale for change	Adaption for the Glioblastoma Cohort D and the RANO criteria
Section to be changed	7.3.2.2 Secondary endpoint analyses for Part 2
Description of change	
Change From: Disease control (DC) will be analyzed in terms of DC rate (DCR), defined as the proportion of patients with best overall response of CR, PR, or SD according to RECIST 1.1. Proportions will be presented with 95% two-sided confidence interval using the exact Clopper-Pearson method.
 
Duration of objective response (DoR) - for all patients with an OR, the duration of OR is defined as time from first documented CR or PR to the earliest of disease progression or death among patients with OR. If a patient did not die or progress until the last visit in the study, this

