Description of change	
Change from: The primary endpoint is the shrinkage estimator of objective response (OR) based on BHM. OR is defined as best overall response (RECIST 1.1) of complete response (CR) or partial response (PR) from first treatment infusion until the earliest of disease progression, death or last evaluable tumor assessment before start of subsequent anti-cancer therapy, lost to follow-up, or withdrawal of consent.
 
To: The primary endpoint is Objective Response (OR) defined as best overall response (RECIST 1.1) of complete response (CR) or partial response (PR) from first treatment infusion until the earliest of disease progression, death or last evaluable tumor assessment before start of subsequent anti-cancer therapy, lost to follow-up, or withdrawal of consent.

Rationale for change	Consistency with Section 2.1.2
Section to be changed	CLINICAL TRIAL PROTOCOL SYNOPSIS (Secondary endpoints):

Description of change	
Change from:
 
PART 1:
 
• Pharmacokinetic parameters C_{max}, t_{max}, AUC_{0-504h} after the first infusion cycle. 
PART 2:
 
• - Pharmacokinetic parameters C_{max}, t_{max}, AUC_{0-504h} after the first and fourth infusion cycle. 
To:
 
PART 1:
 
• Pharmacokinetic parameters C_{max}, t_{max}, AUC_{0-504h} after the first and fourth infusion cycle. 
PART 2:
 
• Pharmacokinetic parameters C_{max}, t_{max}, AUC_{0-504h} after the first infusion cycle.
Rationale for change	Updated timepoints to be in line with section 2.
Section to be changed	CLINICAL TRIAL PROTOCOL SYNOPSIS 3.1 OVERALL TRIAL DESIGN AND PLAN 3.3 SELECTION OF TRIAL POPULATION 7.4 INTERIM ANALYSES 7.7.2 Determination of sample size for Part 2
Description of change	Number of patients updated from 293 to 420 screened and from 230 to 290 evaluable patients (treated) in Part 2.
Rationale for change	Number of patients updated due to the addition of cohort H and 30 additional patients in cohort F.
Section to be changed	FLOW CHART (PART 2) 2.2.2 Further endpoints 6.2.5.2 Follow up for Overall Survival
Description of change	Adding Overall Survival as a further endpoint and the Follow up for Overall Survival status visit
Rationale for change	Data collection for new Further endpoint in Part 2

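### The radiotherapy rule in Protocol 4.2.2 stops later unequivocal growth of an irradiated non-target lesion from counting as progression, so PFS and DoR may be overstated

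*Protocol*

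**What the plan says.** The rule is in Protocol section 11.4 (Global Amendment 4), new text of 4.2.2:

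- Timing: "Palliative radiotherapy will not be allowed during the first cycle for any lesion".
- Scope: "Palliative radiotherapy is allowed only for non-target lesions, following discussion with the Medical Monitor". A later sentence waives prior contact with the Medical Monitor in emergencies.
- Condition: "provided that the reason for radiotherapy does not reflect PD and does not interfere with response assessment".
- Consequence: an irradiated lesion is declared not evaluable from then on and "may not be included in the assessment of the non-target lesions and the overall assessment".

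The sentence makes no exception for growth. In the part of the protocol at hand, the only later listed change to 4.2.2 is the corticosteroid wording for cohort D in section 11.5 (Amendment 5), so the radiotherapy text reads as standing.

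On assessment, the Amendment 4 text of 7.3.1.2 defines confirmed response "according to RECIST 1.1 for all cohorts except GBM as assessed by the Investigator", with RANO for glioblastoma. Section 5.1 (same amendment) has a CRO collect and store all imaging, and adds "The CRO will not be implicated in tumor response evaluation". Central review at a later time is left open.

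**The concern.** Radiotherapy can shrink a lesion whatever the study drugs do, so an irradiated lesion should not help a patient towards response. That argument runs in one direction only: it gives no reason to ignore a lesion that grows in spite of radiotherapy. The rule is symmetric. It takes the lesion out of the non-target judgement and out of the overall response, so an investigator who follows it has no way to record PD on that lesion.

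What is at stake is mainly the time endpoints. In sections 2.1.3 and 7.3.2.2 (Amendment 4 text), PFS and DoR end at progression or death. A missed progression lengthens both. The trial has no control arm in which the same omission would occur, and its results are read against published rates.

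**Working it through.** The protocol gives no figure for this rule, so there is none to reproduce. The check is of the text, followed by an illustrative bound.

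**Step 1. Which lesions fall into the gap.**

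| Situation | Treatment in the text of 4.2.2 |
|---|---|
| Target lesion | Radiotherapy not permitted |
| Any lesion, cycle 1 | Radiotherapy not permitted |
| Non-target lesion whose need for radiotherapy reflects PD | Outside the permission |
| Non-target lesion not reflecting PD, irradiated, then shrinks | Excluded: no response credit, as it should be |
| Non-target lesion not reflecting PD, irradiated, then grows unequivocally | Excluded: cannot be PD |

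The last row is the defect. The condition about PD governs whether radiotherapy may be given. It says nothing about what happens afterwards, and the exclusion applies to any exposed lesion. Progression in target lesions, in other non-target lesions or by new lesions still counts, as does death. The rule therefore matters only when the irradiated lesion is the first or only site of progression.

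**Step 2. Endpoint by endpoint.**

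- *PFS and DoR.* Both run until progression or death. If the irradiated lesion progresses first, the recorded time runs on to the next event or to censoring. These are the most exposed.
- *Disease control.* Imaging was every 6 weeks, that is, every two cycles, and only cycle 1 is barred. Radiotherapy in cycle 2 can precede the first scan, so early growth confined to that lesion can leave SD as best response. Exposed, but less so.
- *ORR.* The target-lesion sum that drives PR is untouched. The response window closes at progression, death or "last evaluable tumor assessment before start of subsequent anti-cancer therapy" (synopsis, Amendment 6 text), and response must be confirmed. A false responder needs radiotherapy after cycle 1, then unequivocal growth of that lesion alone, before response is reached or confirmed, while the targets shrink to PR. Growth after a confirmed response does not undo it.

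**Step 3. Illustrative size.** Let *q* be the share of patients irradiated on study and *g* the share of those in whom the irradiated lesion is the first or only progression site. Neither is in the documents; the ranges below are assumptions.

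- Upper limit of the shift in a rate = *q* × *g*.
- Ratio of median PFS, with exponential PFS and that part of the hazard fully suppressed = 1 / (1 − *q* × *g*).

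| *q* | *g* | *q* × *g* | Patients of 30 | Median PFS ratio |
|---|---|---|---|---|
| 2% | 10% | 0.2 points | 0.06 | 1/0.998 = 1.002 |
| 5% | 25% | 1.25 points | 0.38 | 1/0.9875 = 1.013 |
| 15% | 50% | 7.5 points | 2.25 | 1/0.925 = 1.081 |

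For scale, one patient is 1/30 = 3.3 points or 1/40 = 2.5 points of a cohort rate. The *q* × *g* column is a ceiling for disease control. For ORR it is far too high, because of the sequence of events required in step 2.

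**The case against.** The best defence is the sentence just before the exclusion. Radiotherapy is for non-target lesions only, never in cycle 1, after discussion with the Medical Monitor except in emergencies, and only when the reason is not progression and response assessment is not disturbed. This stands against two stronger readings. A reader might infer that a lesion already progressing can be irradiated and dropped; the permission does not cover it. A reader might also infer that the open-label investigator alone decides; the text requires the sponsor-side discussion, and stored images may still go to central review. The defence does not reach growth after radiotherapy.

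A reader might add that the rule lets a patient be called CR with disease remaining at the irradiated site. Even so, none of the four endpoints moves: ORR and disease control count CR and PR alike, DoR starts at the first of either, and PFS does not depend on the distinction.

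It is also fair to say that handling of radiotherapy in the PFS and DoR analyses belongs to an SAP, which is not shown. That stands for analysis rules. It does not answer the lesion rule, which the protocol itself fixes: an analysis cannot use a progression that investigators were told not to record.

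Finally, section 11.7 (Amendment 7, text for 1.3) reports that enrolment was complete and that efficacy showed no clear improvement over standard of care, apart from one possibly promising cohort that was judged confounded. The practical consequence is therefore limited to how the results are reported.

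**Conclusion.** The point holds in a narrow form. As written, unequivocal later growth of an irradiated non-target lesion cannot be called PD. PFS and DoR may be overstated, disease control less so, and ORR only in a rare sequence of events. The documents do not support a claim that all four endpoints are biased upward: the direction of a missed progression is clear, but whether any occurs depends on how often radiotherapy is given and how often that lesion progresses first, and neither is stated. The effect is probably small: at most 0.2 to 7.5 points on a rate and a median PFS ratio of 1.002 to 1.081 over the assumed ranges.

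Two limits apply. The conclusion rests on the amendment log, since the body text of 4.2.2, 5.1 and 7.3 lies in the part not shown. It chiefly concerns the cohorts read by RECIST 1.1, because cohort D uses RANO and excludes extracranial disease.

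**What to change.** Reword the sentence in 4.2.2 to say three things: an irradiated non-target lesion stays on the lesion list; it is not evaluable for response; and it still counts as PD if it progresses unequivocally. Apply this reading to the images already collected for patients who had on-study palliative radiotherapy. Who may receive radiotherapy, and when, is not affected.

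The cost is one sentence and a re-check of the affected patients' scans. Swelling after radiotherapy will need the usual judgement of what is unequivocal, and a few PFS or DoR times will shorten. After the interim data cut-off, imaging follows institutional practice (section 11.7, text for 5.1), so late growth may be dated less precisely.

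Counting the start of radiotherapy itself as an event is not part of this fix. By the protocol's own condition the radiotherapy did not reflect PD, so that analysis would err the other way, and the choice belongs to the SAP.
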